12.3. Appendix 3: Study Phases and Treatment Emergent Adverse Events

12.3.1. Treatment Phases

Treatment phases are defined for the purpose of AE summaries and listings.

AEs will be assigned to pre-treatment, on-treatment, and post-treatment phases according to the date/time of occurrence relative to Dates/Times of First and Last Doses of Study Drug.

Treatment Phase	Definition
Pre-Treatment	Date/Time of AE < First Dose Date/Time of Study Drug ¹
On-Treatment	First Dose Date/Time of Study Drug ¹ ≤ Date/Time of AE ≤ Last Dose Date/Time of Study Drug ² + 56 Days
Post-Treatment	Date/Time of AE > Last Dose Date/Time of Study Drug ² + 56 Days

¹Earliest dose of GSK2315698 or GSK2398852 or 89Zr-GSK2398852 in the study

²Latest dose of GSK2315698 or GSK2398852 or 89Zr-GSK2398852 in the study

Unless stated otherwise, AE summaries will only include AEs assigned to the on-treatment phase. All AE listings will include treatment phase assignment.

12.3.2. Treatment Sessions

Treatment sessions are defined for the purpose of AE listings.

AEs will be assigned to treatment sessions according to the time of occurrence relative to Dates/Times of First and Last Doses of Study Drug for each treatment session.

Treatment Sessions	Definition
Treatment Session 1	Session 1 First Dose Date/Time of Study Drug ¹ ≤ Date/Time < Session 2 First Dose Date/Time of Study Drug ¹ or ≤ Session 1 Last Dose Date/Time of Study Drug ² + 56 Days (if Session 2 is not applicable).
Treatment Session 2	Session 2 First Dose Date/Time of Study Drug ¹ ≤ Date/Time ≤ Session 2 Last Dose Date/Time of Study Drug ² + 56 Days

¹Earliest treatment session dose of GSK2315698 or GSK2398852 or ⁸⁹Zr-GSK2398852

²Latest treatment session dose of GSK2315698 or GSK2398852 or ⁸⁹Zr-GSK2398852

12.3.3. AE Onset Time and Duration

The following AE onset times and duration will be included in all AE listings.

	Definition
AE Onset Day Since First Dose of Study Drug ¹ (Days)	If First Dose Date/Time of study drug ¹ > AE Onset Date/Time, Onset Day = AE Onset Date - First Dose Date If First Dose Date/Time of study drug ¹ ≤ AE Onset Date/Time, Onset Day = AE Onset Date - First Dose Date + 1 Day Missing if subject is not exposed to any study drug
AE Onset Day Since Treatment Session First Dose of CPHPC (Days)	If Session CPHPC First Dose Date/Time of study drug > AE Onset Date/Time, Onset Day = AE Onset Date – Session CPHPC First Dose Date If Session CPHPC First Dose Date/Time of study drug ≤ AE Onset Date/Time, Onset Day = AE Onset Date – Session CPHPC First Dose Date + 1 Day Missing if AE not assigned to treatment session
AE Onset Day Since Treatment Session First Dose of mAb (Days)	If Session mAb First Dose Date/Time of study drug > AE Onset Date/Time, Onset Day = AE Onset Date – Session mAb (labelled or unlabelled) First Dose Date If Session mAb First Dose Date/Time of study drug ≤ AE Onset Date/Time, Onset Day = AE Onset Date – Session mAb (labelled or unlabelled) First Dose Date + 1 Day Missing if AE not assigned to treatment session
Duration (Days)	AE Resolution Date – AE Onset Date + 1
Drug-related	If relationship is marked 'YES' on Inform/CRF OR value is missing.

¹Earliest dose of GSK2315698 or GSK2398852 or 89Zr-GSK2398852 in the study

12.4. Appendix 4: Data Display Standards & Handling Conventions

12.4.1. Baseline Definitions

For all endpoints, the baseline value used for descriptive summaries and listings will be the latest assessment prior to first administration of anti-SAP treatment.

The first administration of anti-SAP treatment will be defined as the first administration of either study drug, i.e. CPHPC or anti-SAP mAb (labelled or unlabelled).

Derivations and Handling of Missing Baseline Data

Definition	Reporting Details
Change from Baseline	= Post-Dose Visit Value – Baseline
Maximum Change from Baseline	= Calculate the change from baseline at each given timepoint after baseline (over treatment sessions and follow up period) and determine the maximum change

NOTES :

- Unless otherwise specified, the baseline definitions specified in Section 12.4.1 will be used for derivations for endpoints / parameters and indicated on summaries and listings.
- Unless otherwise stated, if baseline data is missing no derivation will be performed and will be set to missing.
- The baseline definition will be footnoted on all change from baseline displays.

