## **5.9. Length of Time Between Dosing Sessions**

There must be a minimum of 4 weeks between each dose of anti-SAP mAb, to allow for plasma SAP levels to return to baseline.

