2.3. Study Objective(s) and Endpoint(s)

Objectives	Endpoints
Primary Objectives	Primary Endpoints
Assessment of ⁸⁹ Zr-GSK2398852 cardiac uptake as evaluated by PET imaging at different mass doses	Standardized Uptake Values (SUV) [i.e. Radioactivity concentrations] in focal anatomical locations within the heart, as well as SUV of the whole heart at different time points after ⁸⁹ Zr-GSK2398852 administration and at different anti-SAP mAb TMDs.
Secondary Objectives	Secondary Endpoints
Assessment of ⁸⁹ Zr-GSK2398852 biodistribution in non-cardiac tissues and organs	Focal and total radioactivity uptake (including, but not limited to SUV) in different tissues (including potentially at those peripheral tissue sites where TTR amyloid deposition can be clinically occult) at different time points and after different TMDs.
Characterisation of the plasma pharmacokinetics of total mAb (unlabelled GSK2398852 and ⁸⁹ Zr-GSK2398852)	Descriptive pharmacokinetic (PK) parameters, including the maximum concentration in plasma (C _{max}), the time associated with C _{max} (T _{max}), clearance, terminal half-life (T _{1/2}) and the area under the concentration-time profile (AUC).
Characterisation of the plasma pharmacokinetics of radioactivity (⁸⁹ Zr-GSK2398852 radio-PK)	Descriptive PK parameters including C _{max} , T _{max} , clearance, T _{1/2} and AUC based on scintillation counter.
Safety & tolerability of Anti-SAP treatment including administration of ⁸⁹ Zr-GSK2398852	All adverse events (AEs) including the incidence and grading of skin rashes, cardiac adverse events and infusion-related reactions, as well as other AEs utilizing standard pharmacovigilance practices.

Objectives	Endpoints
	Absolute changes in safety lab parameters, including cardiac troponin and N-terminal prohormone of brain natriuretic peptide (NT-ProBNP). Other safety information, including electrocardiogram (ECG), inpatient and outpatient cardiac telemetry, vital signs, and physical exam data.
Exploratory Objectives	Exploratory Endpoints
Correlation of regional pattern of ⁸⁹ Zr-GSK2398852 uptake in the heart with the pattern of amyloid load by PiB scan and blood flow by WAT scan or MRI signal pattern	Maps of regional PET signals or MRI signals over the myocardium will be visually compared and scored. Regional derived PET and MRI parameters correlated within and across ATTR-CM patients.

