12.2. Appendix 2: Schedule of Activities

12.2.1. Protocol Defined Schedule of Events

Table 9 Part A and Part B Overview

	Dosing Session 1	Dosing Session 2
Part A	X	X
Part B	X	

Table 10 Overview All Groups

	Screening ¹	Baseline ²	Dosing Sessions 1 and 2																		
			Day 1: pre- dose	Day 1	Day 2	Day 3: pre-dose mAb	Day 3: anti-SAP mAb dosing	Day 3: end of mAb infusion ¹⁸	Day 3: 4 hours post end mAb infusion ¹⁸	Day 4	Day 5	Day 6	Day 7	Day 8	Day 9	Day 10	Day 11	Day 11-18	Day 20 ¹⁸	Day 26 ^{16, 18}	
Inpatient stay at unit			-----X-----																		
Discharge from inpatient																	X				
Outpatient visit	X	X																		X	
Remote Contact for Safety Assessment																			X		
Informed consent	X																				
Medical history/risk factors/demographics	X																				
Inclusion/exclusion criteria	X																				
Safety Assessments																					
Physical examination ³	X		X			X		X			X			X			X				
Adverse event (AE)/ serious adverse event (SAE) Assessment			-----X-----																		
Concomitant Medications			-----X-----																		
12-lead electrocardiogram (ECG)	X ¹³		X ¹³		X	X		X	X	X	X	X	X	X	X	X	X		X ²¹	X	
Continuous Lead II Telemetry ²⁰			-----X-----																		

		Dosing Sessions 1 and 2																			
	Screening ¹	Baseline ²	Day 1: pre-dose	Day 1	Day 2	Day 3: pre-dose mAb	Day 3: anti-SAP mAb dosing	Day 3: end of mAb infusion ¹⁸	Day 3: 4 hours post end mAb infusion ¹⁸	Day 4	Day 5	Day 6	Day 7	Day 8	Day 9	Day 10	Day 11	Day 11-18	Day 20 ¹⁸	Day 26; ^{16, 18}	
Remote Continuous Cardiac Monitoring ⁴		X															X	X			
Vital signs	X ₁₃		X		X	X		X	X	X	X	X	X	X	X	X	X	X		X ₂₁	X
Screening Laboratory Assessments ⁵	X																				
Haem/clin chem/urinalysis	X		X			X					X		X				X				X
Troponin T/ N-terminal prohormone of brain natriuretic peptide (NT-ProBNP)	X		X		X	X				X	X	X	X	X	X	X					X
Pregnancy Test	X ₁₅		X ₁₅																		
Investigational medicinal product (IMP) Administration																					
Carboxy pyrrolidine hexanoyl pyrrolidine carboxylate (CPHPC) IV																					
CPHPC SC ¹²								X ₁₁		X	X	X	X	X	X	X	X				
Premedication (hydrocortisone/anti-histamine)						X															
Unlabelled anti-SAP mAb							X ₇														
⁸⁹ Zr-GSK2398852							X ₇														
Pharmacokinetics (PK)/SAP ⁹																					
Blood sampling for plasma SAP			X		X ₆																
Anti-SAP mAb PK ¹⁷							X	X	X	X	X	X	X								

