12.5.4. Triplicate ECG and Vital Sign measurements

ECG measurements are performed in triplicate at Screening and at the Day 1 Pre-dose timepoint of each dosing session. Vital signs are performed in triplicate at screening. The average of the triplicate measurements will be used for all summary tables, whereas individual measurements will be displayed in figures and listings. As a consequence, the average of the 3 Session 1 Day 1 Pre-dose measurements will be used as the baseline value for ECG summary tables. In case of missing Session 1 Day 1 Pre-dose ECG measurement, the average of the 3 Screening values will be used as the baseline value instead.

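### Session 2 safety changes are referred only to the pre-treatment baseline; a session-specific change should be added beside it, chiefly for the maximum-QTc and worst-case shift tables

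*SAP*

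**What the plan says.** SAP 12.4.1 sets the baseline for every endpoint: "the baseline value used for descriptive summaries and listings will be the latest assessment prior to first administration of anti-SAP treatment". It explains that the first administration is "defined as the first administration of either study drug", with no reference to session. Maximum change is the largest change at any time point after baseline, "over treatment sessions and follow up period".

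SAP 12.5.4 leaves no doubt about the reading for ECG. It notes that "ECG measurements are performed in triplicate at Screening and at the Day 1 Pre-dose timepoint of each dosing session", and then says that "the average of the 3 Session 1 Day 1 Pre-dose measurements will be used as the baseline value for ECG summary tables", with the Screening mean as fallback.

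The schedule in SAP 12.2.1 places its day columns under the header "Dosing Sessions 1 and 2". The Day 1 pre-dose column is marked for ECG, vital signs, haematology/chemistry/urinalysis and troponin T/NT-proBNP. A fresh pre-dose set is therefore planned for Session 2.

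The endpoint concerned is a stated secondary one (SAP 2.3): "Absolute changes in safety lab parameters, including cardiac troponin" and NT-proBNP, with ECG and vital signs as other safety information. On spacing, Protocol 5.9 says: "There must be a minimum of 4 weeks between each dose of anti-SAP mAb".

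Elsewhere the SAP does use session-specific references: for assigning AEs and computing their onset day (12.3.2, 12.3.3), for exposure (Tables 1.13 and 1.14) and for vital-sign plots (Figure 3.1). No session-specific baseline for change appears anywhere in it.

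**The concern.** A Part A subject may receive up to two total mass doses, and Protocol 10.3.4 allows the unlabelled dose to be escalated at the second session. A safety reader will want to know what happened after each dose. Under the SAP rule, Session 1 change is measured from a value taken about two days before the antibody. Session 2 change is measured from that same value, by then a month or more old. The two columns look alike but answer different questions.

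The protocol itself gives short-term and longer-term movements different meanings. Section 3.2.1 treats a transient NT-proBNP rise as possible target engagement in the heart. Section 9.8.1 treats a fall from baseline as possible evidence of amyloid clearance. A Session 2 change from the Session 1 reference adds the two together.

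The maximum-change rule goes one step further. The Session 2 pre-dose value is itself a time point after baseline, so it could set a subject's maximum QTc increase before the second session's treatment begins. These tables are also interim deliverables, seen before the decision on Part B.

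**Working it through.** The plan gives no figure to reproduce: sample size rests on feasibility and no hypothesis is tested. The check is date arithmetic, a decomposition of the change, and a review of the displays.

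**Timing.** Inputs: baseline on Session 1 Day 1; antibody on Day 3, or Day 4 with the permitted one-day delay (Protocol 5.4); at least 28 days between antibody doses (Protocol 5.9).

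- Without delay, the second antibody dose falls on study day 3 + 28 = 31 at the earliest, which is 31 − 1 = 30 days after baseline.
- Session 2 Day 1 is then study day 31 − 2 = 29, which is 28 days after baseline. One-day delays give 27 to 29.
- Session 2 Day 26 is study day 29 + 25 = 54, which is 53 days after baseline. One-day delays give 52 to 54, before the ±2 day visit window.
- With a Session 2 pre-dose reference, the distance to the second antibody dose is 2 days (3 if delayed) instead of at least 30.

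**Decomposition.** Let B1 and B2 be the Session 1 and Session 2 pre-dose values, and Y2 a Session 2 post-dose value.

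Y2 − B1 = (B2 − B1) + (Y2 − B2)

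The left side is what the SAP reports. The first term on the right is drift or carry-over; the second is acute change. B2 is collected, so the split needs no new measurement.

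**Which displays allow the split.**

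| Display | Can acute Session 2 change be recovered? |
|---|---|
| Troponin T/NT-proBNP (Listing 35) | Yes: value and change by subject, period and visit |
| ECG change by visit (Table 3.20) | Mean only, by subtracting visits, if the same subjects contribute at both |
| Vital signs (Figure 3.1) | By eye, panelled by subject and session |
| Maximum QTc and maximum QTc increase (Tables 3.19, 3.21) | No |
| Worst-case laboratory shifts (Tables 3.10, 3.12, 3.15) | No |
| Numeric laboratory and ECG listings (25, 26, 28, 29) | Only for subjects with a value of potential clinical importance (PCI) |

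Listings 27 and 30 add character laboratory results and abnormal ECG findings.

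**Illustration on the SAP's own QTc flag** (increase above 60 msec, SAP 12.7.4). The documents give no drift value, so the drifts and acute changes here are assumed.

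| Drift (msec) | Acute change (msec) | From Session 1 baseline | From Session 2 baseline |
|---|---|---|---|
| +20 | +50 | 70, flagged | 50, not flagged |
| 0 | +65 | 65, flagged | 65, flagged |
| −20 | +65 | 45, not flagged | 65, flagged |

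The result can go either way. In the last row the subject also stays out of the PCI-based ECG listings, unless another ECG criterion brings that subject in.

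**Noise.** Let r be the SD of between-session drift divided by the within-session SD, with drift independent of within-session error. The SD of Session 2 change rises by √((2 + r²)/2). For an assumed r of 0.5 to 2 this is √(2.25/2) = 1.06 to √(6/2) = 1.73.

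**The case against.** The strongest reply is that a pre-treatment baseline is the only untreated reference in the study. A Session 2 pre-dose value may hold residual effect from Session 1, which a session baseline would subtract away. The study baseline is also disclosed by footnote on change displays, and it agrees with Protocol 9.3.4.1, which compares electrophysiology after Session 1 with Screening. All of this stands. A reader might infer that the study baseline is an error; the documents do not support that, because it is the right reference for cumulative change.

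A reader might also infer that Session 2 changes are uninterpretable. That goes too far, given the listing, by-visit table and plots set out above. In addition, SAP 3.1 promises individual profiles, listings and tabulations where appropriate at the end of Part A, covering blood pressure, heart rate, chemistry, haematology, NT-proBNP and troponin T. Appendix 9 does not itemise all of these, however, and ECG intervals are not named in that list.

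Third, the safety objective is overall tolerability. Summary columns are by study part, and no display claims to isolate a second-dose effect. That limits the weight of the point but does not remove it: the session split is cheap, and the maximum and worst-case tables cannot supply it.

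Finally, not every Part A subject need have two sessions. The plan says up to two, and Protocol 5.11 lets a subject with one session count as having completed.

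**Conclusion.** The point holds as a worthwhile, low-cost addition to the SAP, not as a fault in the study baseline. It concerns at most 3 subjects, all in Part A; Part B has a single session. No test or error rate changes, and AE summaries and listings are untouched.

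For those subjects, Session 2 change is taken from a reference at least about 30 days before the second antibody dose and combines drift or carry-over with acute change. The loss is real where the planned output cannot be differenced: the maximum-QTc, maximum-QTc-increase and worst-case shift tables, and numeric laboratory and ECG data for subjects without a PCI value.

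The timing rests on the protocol's minimum interval. The QTc and SD illustrations rest on assumed drift. It would be tempting to state a percentage distortion, but the documents do not allow it: the SAP defines change as a difference, and neither document gives a drift figure. Subjects must also have been clinically stable for at least 3 months before Screening, so drift may be small.

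**What to change.** Keep the 12.4.1 baseline for cumulative change. Add a second, session-specific baseline, defined as the last value before that session's first CPHPC dose, using the triplicate mean for ECG. Apply it to laboratory tests, troponin T/NT-proBNP, ECG/QTc and vital signs, and show both changes side by side because the Session 2 pre-dose value may carry residual Session 1 effect. For Session 1 the two baselines coincide.

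Present the maximum-QTc, maximum-QTc-increase and worst-case shift displays by session as well as overall, so that a Session 2 pre-dose value cannot stand as a Session 2 maximum. State whether a missing Session 2 Day 1 pre-dose value is replaced by the Session 1 Day 26 value or left missing.

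The cost is a few lines in SAP 12.4.1 and 12.5.4, one derived column, and by-session versions of a handful of tables. No new data are needed. The change concerns reporting only and leaves the protocol's stopping criteria as they are.

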12.4.2. Reporting Process

Software	

 • The currently supported versions of SAS software will be used. 	
Reporting Area	
HARP Server	: uk1salx00175
HARP Compound	: \arprod\gsk2398852\mid204512\final
Analysis Datasets	

 • Analysis datasets will be created according to CDISC standards. 	
Generation of RTF Files	

 • RTF files will be generated for all the tables 	

12.4.3. Reporting Standards

General	

 The current GSK Integrated Data Standards Library (IDSL) will be applied for reporting, unless otherwise stated (IDSL Standards Location: https://spope.gsk.com/sites/IDSLLibrary/SitePages/Home.aspx): 
 4.03 to 4.23: General Principles 5.01 to 5.08: Principles Related to Data Listings 6.01 to 6.11: Principles Related to Summary Tables 7.01 to 7.13: Principles Related to Graphics 	
Formats	

 GSK IDSL Statistical Principles (5.03 & 6.06.3) for decimal places (DP's) will be adopted for reporting of data based on the raw data collected, unless otherwise stated. Numeric data will be reported at the precision collected on the eCRF. The reported precision from non eCRF sources will follow the IDSL statistical principles but may be adjusted to a clinically interpretable number of DP's. 	
Planned and Actual Time	

 Reporting for tables, figures and formal statistical analyses: 
 Planned time relative to dosing will be used in summary figures, summaries, statistical analyses and calculation of any derived parameters. The impact of any major deviation from the planned assessment times and/or scheduled visit days on the analyses and interpretation of the results will be assessed as appropriate. Actual times relative to the first study dose of anti-SAP treatment (CPHPC or labelled mAb or unlabelled mAb) will be used in individual subject plots Reporting for Data Listings: 
 Planned and actual time relative to study drug dosing (first dose of either GSK2315698 or anti-SAP mAb (labelled and unlabelled)) will be shown in listings (Refer to IDSL Statistical Principle 5.05.1). 	
Unscheduled Visits	

 Unscheduled visits will be used for baseline derivations in summary tables. Post-baseline unscheduled visits will not be included in summary tables, with the exception of the following summaries: Summary of Hematology/Chemistry/ Urinalysis Shifts from Baseline Relative to normal range (worst case post baseline). Summary of Haemoglobin Change from Baseline Relative to Clinical Importance Range, Summary of Maximum QTc Values Post-Baseline Relative to Baseline by Category, Summary of Maximum Increase in QTc Values Post-Baseline Relative to Baseline by Category, Summary of hepatobiliary laboratory abnormalities, Summary of ECG findings. All unscheduled visits will be included in individual subject plots. All unscheduled visits will be included in listings. 	
Descriptive Summary Statistics	
Continuous Data	Refer to IDSL Statistical Principle 6.06.1
Categorical Data	N, n, frequency, %
Graphical Displays	

 Refer to IDSL Statistical Principals 7.01 to 7.13. 	

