### 5.3.1. Timing of Zr-GSK2398852 PET scans

Up to three serial Zr-GSK2398852 PET scans will be performed during each dosing session.

For the 1st subject in Part A, PET scans for each dosing session will be performed at the following times in relation to administration of the Zr-GSK2398852 infusion on Day 3:

**1st PET scan:** Day 3 → 5 ± 2 hours from the end of Zr-GSK2398852 infusion

**2nd PET scan:** Day 4 → 24 ± 4 hours from the end of Zr-GSK2398852 infusion

**3rd PET scan:** Day 6 → 72 ± 6 hours from the end of Zr-GSK2398852 infusion

[figure not shown]
For subsequent subjects in Part A and Part B, the timing and number of the PET scans may be varied after the 1st subject in Part A has completed both dosing sessions based on emerging SUV & radiolabel PK data. This information will be communicated to the site in a file note prior to the start of each subsequent dosing session.

Further details on PET procedures and analyses are given in the Imaging Acquisition and Analysis Manual.

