### 5.4. Administration of CPHPC

Subjects will begin IV CPHPC infusion on Day 1 and continue the infusion for a minimum of approximately 48 hours until Day 3. The infusion will be stopped prior to the anti-SAP mAb infusion. It is critical that the subject's plasma SAP level is below the target prior to beginning the anti-SAP mAb infusion.

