**Figure 3 IV CPHPC Infusion Schematic**

SC CPHPC injections will be administered thrice daily, with the first SC CPHPC dose administered approximately 5 hours after the end of the IV CPHPC infusion. It is possible this may overlap with anti-SAP mAb administration.

**It is important that the SC CPHPC doses are administered after the administration of anti-SAP mAb to ensure circulating SAP remains low to prevent the formation of large amounts of anti-SAP mAb / SAP immune complex formation, even if the subject withdraws from the study.**

If a subject is unable to tolerate SC CPHPC injections, the investigator should consider administration of CPHPC via an IV infusion.

If anti-SAP mAb dosing is delayed (e.g. due to PET scanner availability or delay in Zr-GSK2398852 transport), the subject may continue IV CPHPC infusion for an additional day. Should this occur, an additional plasma SAP specimen should be collected, and the result confirmed to be below target prior to administering anti-SAP mAb, in effect repeating all Day 2 procedures. This should only be done if logistics permit and PET camera availability is confirmed.

Should the delay be any longer than 1 day, IV CPHPC administration will be stopped, and subject may be invited to return at a later date to re-start the dosing session. The Medical Monitor should be notified in such instances.

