**Table 6 Proposed Duration and Timing of anti-SAP mAb and Zr-GSK2398852 administration**

Total Mass Doses of anti-SAP mAb	Proposed Duration of Unlabelled anti-SAP mAb Infusions	Planned Timing of  Zr-GSK2398852 Administration in Relation to Unlabelled anti-SAP mAb Infusion 
80 – 200 mg	1 Hour	Simultaneous administration: Both infusions administered over 1 hour & finishing at approximately the same time 
200 mg < Total Mass Dose ≤500 mg	6 Hours	Co-administration:  Zr-GSK2398852 administered over 1 hour, commencing any time after start of unlabelled anti-SAP mAb, including after its completion

If a subject experiences infusion reaction, dosing may be paused and resumed at investigator discretion.

Unlabelled anti-SAP mAb and Zr-GSK2398852 will be administered via two separate peripheral venous lines

After the first subject, there is an option (based on emerging data) that administration of Zr-GSK2398852 may be initiated at any time during the infusion or after the unlabelled anti-SAP mAb infusion has completed.

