7. PRIMARY STATISTICAL ANALYSES

7.1. Primary Analyses

7.1.1. Endpoint / Variables

- Standardized Uptake Values (SUV) [i.e. Radioactivity concentrations] in focal anatomical locations within the heart, as well as SUV of the whole heart at different time points after ⁸⁹Zr-GSK2398852 administration and at different anti-SAP mAb TMDs.

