12.5. Appendix 5: Derived and Transformed Data

12.5.1. General

Multiple Measurements at One Analysis Time Point

 • Mean of the measurements will be calculated and used in any derivation of summary statistics but if listed, all data will be presented. • Subjects having both High and Low values for Normal Ranges at any post-baseline visits for safety parameters will be counted in both the High and Low categories of “Any visit post-baseline” row of related summary tables. This will also be applicable to relevant Potential Clinical Importance summary tables.
Study Day

 • Calculated as the number of days from the first study dose of aSAP treatment (GSK2315698 or labelled mAb or unlabelled mAb): 
 • Ref Date or Study Dose Date = Missing → Study Day = Missing • Ref Date < aSAP treatment first study Dose Date → Study Day = Ref Date – aSAP treatment First Study Dose Date • Ref Data ≥ aSAP treatment first study dose date Dose Date → Study Day = Ref Date – (aSAP treatment First Study Dose Date) + 1

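### SAP 12.4.3 times the PET plots and listings from the first CPHPC dose rather than the tracer, and the displays carrying the primary endpoint name neither total mass dose nor hours since tracer

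*SAP*

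**What the plan says.** **Clock in the SAP.** Section 12.4.3 gives individual subject plots "Actual times relative to the first study dose of anti-SAP treatment (CPHPC or labelled mAb or unlabelled mAb". Listings show planned and actual time from the first dose of CPHPC or mAb. Study Day in 12.5.1 has the same origin: "Calculated as the number of days from the first study dose of aSAP treatment (GSK2315698 or labelled mAb or unlabelled mAb". Neither section makes an exception for PET.

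**Clock in the endpoint and design.** SAP 7.1.1 defines the primary endpoint as SUV in focal heart locations "as well as SUV of the whole heart at different time points after" tracer administration, and at different TMDs. Protocol 5.3.1 says of the first subject that "PET scans for each dosing session will be performed at the following times in relation to administration of the" tracer infusion. The times are 5 ± 2 h, 24 ± 4 h and 72 ± 6 h from its end. Later subjects' times may be changed by file note.

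**Order and spacing of doses.**
- Protocol 5.4: "Subjects will begin IV CPHPC infusion on Day 1 and continue the infusion for a minimum of approximately 48 hours until Day 3". If mAb dosing slips, "the subject may continue IV CPHPC infusion for an additional day".
- Protocol Table 6, for TMD above 200 mg: a 1 h tracer infusion "commencing any time after start of unlabelled anti-SAP mAb, including after its completion".
- Protocol 5.9: "There must be a minimum of 4 weeks between each dose of anti-SAP mAb".

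**Displays.** SAP 2.2 removes PET descriptive statistics and grouping by TMD. SAP Table 2 leaves only individual figures and listings for the primary endpoint. Figures 2.1 and 2.2 are panelled by subject and dosing session, with actual time in days on the X axis. Listings 33 and 34 (shells PD_L1 and PD_L2) show planned period and visit, date and Study Day, region or organ, SUV and volume.

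**Ratio.** SAP 7.1.2 takes a cardiac/plasma SUV ratio of at least 0.5 as consistent with uptake. SAP 12.4.5 says tissue SUV has to be related to the concurrent plasma radio-PK.

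**Planned or actual time.** SAP 12.4.3 applies planned time to derived parameters without exception. SAP 9.1.1 bases all non-compartmental parameters on actual sampling times.

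**The concern.** The primary endpoint has two axes, time since tracer and TMD, and the displays that report it show neither by name. The time axis that 12.4.3 does prescribe measures something else: time since SAP depletion began.

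Time since tracer determines how a cardiac SUV is read. Protocol 5.13.2 expects early scans to reflect blood pool and a scan near 72 h to be more likely to show myocardial uptake. The design also depends on comparing the same patient at two mass doses (Protocol 5.12.1.2) and, optionally, on displacement at Session 2 against Session 1 (Protocol 10.3.4). With grouped summaries gone, a reader of the study report has to make those comparisons from the individual plots and listings.

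**Working it through.** **1. The plan's own figure.** Shell PD_L1 prints Study Day 3 for the Session 1, Day 3 scan, which is the tracer day. By 12.5.1, Study Day = scan date − first dose date + 1.
- From CPHPC on Day 1: 3 − 1 + 1 = 3, which matches the shell.
- From the tracer on Day 3 it would be 3 − 3 + 1 = 1.

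So the shells do use the CPHPC origin.

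**2. First CPHPC dose to end of tracer.** Offset = CPHPC lead-in + any unlabelled infusion run before the tracer + 1 h tracer infusion. This assumes that the mAb starts as CPHPC stops.

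| Case | Sum | Offset |
|---|---|---|
| 48 h lead-in, simultaneous 1 h infusions | 48 + 1 | 49 h |
| 48 h lead-in, tracer directly after a 6 h infusion | 48 + 6 + 1 | 55 h |
| One-day extension, tracer directly after a 6 h infusion | 72 + 6 + 1 | 79 h |

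Table 6 sets no latest start for the tracer, so 79 h is an illustrative upper case and not a limit.

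**3. Where nominal scans plot.** Position in days = (offset + hours after tracer) / 24.
- 5 h scan, offset 49 h: 54 / 24 = 2.25 d
- 24 h scan, offset 49 h: 73 / 24 = 3.04 d
- 5 h scan, offset 79 h: 84 / 24 = 3.50 d
- 5 h scan in Session 2, 28 days on, offset 49 h: (49 + 672 + 5) / 24 = 30.25 d

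One subject's 5 h scan can therefore plot after another's 24 h scan (3.50 against 3.04 d). That reversal needs the one-day extension. Without it, the shift in this calculation is 55 − 49 = 6 h, against a gap of 24 − 5 = 19 h between nominal scans, and the order holds.

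**4. What the listings recover.** If dosing slips a day, the note under the schedule of activities repeats Day 2 and moves later assessments by a day. This implies that planned visit Day 3 stays on the tracer day, while Study Day for that scan becomes 4 − 1 + 1 = 4. In Session 2 it is 3 + 28 = 31 or later. The planned visit therefore gives nominal days since tracer and Study Day does not. Neither gives hours, and after the first subject the nominal hours are not fixed in the protocol.

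**5. Planned against actual time.** Protocol Table 5 allows radio-PK samples ± 4 h at 24, 48 and 72 h, for guidance only. Planned and actual times can differ, so 12.4.3 and 9.1.1 can give different parameters from the same data.

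**The case against.** The best defence is that this is a descriptive study with no hypothesis test, and nothing in it is biased by the choice of origin. Each session's offset is constant, so the curve within a subject-session panel keeps its shape. The figures never put two subjects in one panel. The planned visit gives the nominal day since tracer. TMD appears in other outputs: the exposure listing, PK Tables 4.1-4.4, and the Table 4.5 shell, which has dose and planned time by heart region. All of this stands. It makes the fault one of reporting, but it does not put actual tracer-relative time or TMD on the four displays. Table 4.5 is titled as plasma data and has no ratio.

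The PD_F1 drawing is not in the available text, so a dose label or time origin on it cannot be ruled out for the figures. The listing shells are visible.

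On the ratio, the primary endpoint is SUV, and the 0.5 limit informs optional evaluations. The imaging centre derives the PET variables and its manual may hold a rule for the plasma value. The blood-pool columns in PD_L1 also give a rough reading. Wall SUV equal to blood-pool SUV means tissue/plasma = 1 − haematocrit, if the mAb stays out of red cells. That is 0.50 at the SAP's haematocrit of 0.5 but 0.60 at an assumed 0.40. Listing the ratio is therefore an improvement that follows from 7.1.2 and 12.4.5, not the repair of a proven omission.

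A reader might infer more than the documents support:
- *Time after tracer cannot be compared at all.* The planned visit allows comparison by nominal day.
- *The ratio will be distorted by pairing nominal scan and sample times.* No section prescribes that pairing, and 12.4.5 points to the concurrent plasma level.
- *Plasma and tissue units do not match.* SAP 9.1.3 uses molar units for PK, but 12.4.5 expresses organ and blood analyses as SUV.
- *The Part A decision is made without dose information because the mAb exposure displays are final-analysis only.* The sponsor confirms each dose, and PK Tables 4.1-4.4 carry TMD at the interim.

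**Conclusion.** The point holds as a reporting fault in the displays for the primary endpoint. SAP 12.4.3 prescribes a time origin that precedes the end of the tracer infusion by about 49 to 55 h, or about 79 h with the one-day extension. It places the same 5 h scan at 2.25 d in Session 1 and at 30.25 d or later in Session 2. In the available text, Figures 2.1-2.2 and Listings 33-34 name neither TMD nor hours since tracer. SAP 2.2 discloses the loss of summaries and grouping, but not this.

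The loss is confined to actual tracer-relative time and dose when sessions and subjects are compared on these displays. The conclusion rests on the mandated order of dosing, a literal reading of first study dose, and there being nothing to the contrary on the unseen drawing.

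The conflict between 12.4.3 and 9.1.1 is a separate inconsistency. The specific rule in 9.1.1 is the natural one to keep, but the text should say so.

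**What to change.** 1. In SAP 12.4.3, time PET and radio-PK displays in actual hours from the end of that session's 89Zr-GSK2398852 infusion.
2. Add TMD and actual hours since end of tracer to Figures 2.1-2.2 and Listings 33-34.
3. Exempt non-compartmental parameters from the planned-time line, citing 9.1.1.
4. List the cardiac/plasma SUV ratio at each scan, using plasma SUV at the actual scan time. If the imaging manual has a rule for that value, cite and follow it. Otherwise state one, such as log-linear interpolation between the bracketing samples. Flag extrapolation: the last scheduled radio-PK sample is at 72 h, and the first subject's third scan may fall at up to 72 + 6 = 78 h.

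The cost is SAP wording, modest programming and one matching rule agreed with the imaging centre. Protocol 7.6 already records dose times, and the scans and radio-PK samples are scheduled. The downside is a small interpolation error in the listed ratio. No dose, visit or clinical rule changes.
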